3.4.1 Prohibited and/or Restricted Treatments

Prohibited and/or restricted medications taken prior to study drug administration in the study are described in Section 3.3.2. Medications taken within 4 weeks prior to study drug administration and until the end of the Clinical Follow-up Period must be recorded on the case report form (CRF). The following medications are prohibited during the study (unless utilized to treat a drug-related AE):

- Concurrent anti-neoplastic therapy (ie, chemotherapy, immunotherapy regimens, or radiation therapy, standard or investigational). However, the maintenance of the castrate state by ARD therapy is allowed in subjects with CRPC.
- Prior exposure to BET inhibitors
- Exposure to any investigational drug within 4 weeks of or concurrent with study drug administration
- Concomitant use of strong inhibitors of CYP3A4 or strong inducers of CYP3A4.
- Prophylactic use of myeloid growth factors to support neutrophil counts may NOT be used before completion of DLT evaluation period. After the completion of the DLT period, the use

of hematopoietic growth factors is at the discretion of the treating physician, as per institutional guidelines. Subjects with neutropenic fever or infection should be treated promptly and may receive therapeutic colony-stimulating factors if appropriate.

- Immunosuppressive agents
- Immunosuppressive doses of systemic corticosteroids (except as stated in Section 3.3.2)
- Live virus vaccine during the study and for a period of three months after the last dose of study treatment.

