4.5.1 Dose Limiting Toxicities

For the purpose of guiding dose escalation, DLTs will be defined based on incidence, intensity, and duration of AEs for which no clear alternative cause is identified. The DLT evaluation period for dose escalation in Part 1 Schedule A is 32 to 35 days (depending on the exact day of the start of Cycle 2); for Schedules B and C it is 35 days. For Part 1 Schedule A, subjects must receive at least 16 of 21 doses of BMS-986158; for Schedule B at least 17 of the 22 doses; and for Schedule C at least 12 of 15 doses to be considered DLT evaluable for dose escalation decisions. The DLT period for safety assessment of BMS-986158 and, if pursued, nivolumab combination therapy in Part 2 will be 28 days for all schedules which excludes a 7-day period for a single dose as in Cycle 1 in Part 1, to allow similar drug exposure and appropriate comparison of the safety profile between Part 1 and Part 2. For Part 2 safety assessment of the combination therapy (if pursued), subjects must receive at least 15 of 20 doses on Schedule A. If alternate schedules are explored, subjects must receive 16 of 21 doses on Schedule B, and 11 of 14 doses on Schedule C. AEs will be graded according to the NCI CTCAE v4.03. For the purpose of subject management, any AE that meets DLT criteria, regardless of the cycle in which it occurs, will lead to dose interruption. Subjects who withdraw from the study during the DLT evaluation interval for reasons other than a DLT may be replaced at the same dose level. The incidence of DLT(s) during the first cycles of treatment (the DLT evaluation period) will be used in dose escalation decisions and to define the MTD. AEs occurring after the DLT period will be considered for the purposes of defining the recommended Phase 2 dose, upon agreement between the Sponsor/ Medical Monitor and investigators, if the AEs are determined to have no clear alternative cause and are not related to disease progression.

DLT(s) will be defined as any of the following events unless a clear alternative cause is identified:

Non-Hematologic DLT:

Any of the following events will be considered a Non-Hematologic DLT:

- \geq Grade 3 Non-Hematologic toxicity, with the following exceptions.
 - ◆ ≥ Grade 3 electrolyte abnormalities that are not complicated by associated clinical AEs, are not clinically significant, last < 72 hours and either resolve spontaneously or respond to conventional medical intervention

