4.5.2 Guidelines for Dose Modifications

Subjects will be monitored continuously for AEs while on study therapy. Subjects will be instructed to notify their physician immediately for any and all AEs. The criteria presented in this section and Table 4.5.2-1 for dose modifications and delays for BMS-986158 are meant as general guidelines.

- Subjects will continue to receive therapy as long as they have not had disease progression or an AE requiring dose modification, as described below.
- Dose modifications, interruptions, or delays may occur in the setting of lower grade AEs and/or be more conservative than indicated in Table 4.5.2-1 based on the clinical judgment of the investigator, and in consultation with the Sponsor/Medical Monitor.
- For BMS-986158, dose reductions should be to the previous lower dose level, or to a dose level in between the previous dose level and the current dose level, after discussion between Sponsor/Medical Monitor. A decision to remain at the current dose level requires a discussion and an agreement between the investigator and the Sponsor/Medical Monitor.
- If several AEs of varying grade or severity occur simultaneously, the dose modification applied should be the greatest reduction applicable based on the worse grade (or severity) observed among the AEs reported.
- Assessment of causality (chronology, confounding factors such as disease, concomitant medications, diagnostic tests and previous experience with the agent) must be determined and documented by the investigator, prior to dose modification.
- If the same Grade 3 non-hematologic AE recurs despite a dose reduction, a second dose reduction versus discontinuation of the subject from further protocol therapy will be discussed and agreed upon by the Sponsor/Medical Monitor and investigators.
- Subjects who experience a Grade 4 non-hematologic AE will not receive additional protocolrelated therapy and will be removed from study unless discussed and agreed upon by the

Sponsor/Medical Monitor and investigators that it is in the best interest of the subject to receive additional therapy with BMS-986158 (for example, if the subject has demonstrated a response to therapy).

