- No more than 2 dose level reductions of BMS-986158 will be allowed per subject. If a third dose reduction is required, the subject must discontinue BMS-986158 (and nivolumab, if receiving combination therapy based on response to therapy). Dose re-escalation after a dose reduction may occur in limited circumstances (such as a change in attribution of an AE, or if re-escalation is in the best interest of the subject) after discussion and agreement of the Sponsor/Medical Monitor and investigators. The number of dose modifications needed for a subject should be discussed and agreed between the investigator and the Sponsor/Medical Monitor.
- Skipped doses will not be administered within the same cycle.
- For an AE requiring dose modification, BMS-986158 (and nivolumab for subjects receiving combination therapy) should be interrupted to allow recovery from the AE. Re-initiation of study drug cannot occur until AE decreases to ≤ Grade 1 or baseline assessment. In case of delayed recovery to ≤ Grade 1 or baseline (except for alopecia) from treatment-related AEs that results in a delay of treatment for > 30 days, the subject will not receive additional protocol-related therapy and will be removed from study unless discussed and agreed upon by the Sponsor/Medical Monitor and investigators that it is in the best interest of the subject to receive additional therapy with BMS-986158 (for example, if the subject has demonstrated a response to therapy).
- For patients receiving combination therapy, if 1 study drug must be discontinued, the other study drug may be continued as single agent therapy based on discussion with Sponsor/Medical Monitor and the investigator.
- For subjects in Part 2 monotherapy expansion or (if pursued) combination expansion who report an AE requiring dose modification, the dose of BMS-986158 should be reduced from 3.75 mg to 3 mg. See Table 4.5.2-1.

For data collection and analysis purposes, all subjects will continue to be classified by the original treatment arm.

Table 4.5.2-1:DoseEven	Modification Criteria for BMS-986158 Drug-Related Adverse			
Adverse Event	Initial Action	Dose Modification		
Grade 4 febrile neutropenia	Discontinue BMS-986158	Discontinue BMS-986158		
Grade 3 febrile neutropenia	Hold BMS-986158 until return to baseline or Grade 1	1st event: Consider reduction by 1 dose level. 2nd event: Reduce by 1 dose level		

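### The AE-treatment waiver in protocol 3.4.1 also lifts the on-study ban on strong CYP3A4 inhibitors, and no hold or restart rule is tied to the inhibitor

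*Protocol*

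**What the plan says.** Protocol 3.4.1 introduces its list with "The following medications are prohibited during the study (unless utilized to treat a drug-related AE". The exception stands in the lead-in, so it governs every item below, including "Concomitant use of strong inhibitors of CYP3A4 or strong inducers of CYP3A4", which carries no qualifier of its own.

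The dosing rules in 4.5 are driven by the AE:
- 4.5.1: "any AE that meets DLT criteria, regardless of the cycle in which it occurs, will lead to dose interruption".
- 4.5.2, hold: "For an AE requiring dose modification, BMS-986158 (and nivolumab for subjects receiving combination therapy) should be interrupted to allow recovery from the AE".
- 4.5.2, restart: "Re-initiation of study drug cannot occur until AE decreases to ≤ Grade 1 or baseline assessment". If slow recovery from a treatment-related AE is the cause and it is one "that results in a delay of treatment for > 30 days, the subject will not receive additional protocol-related therapy", continuing needs agreement between the Sponsor/Medical Monitor and investigators.
- 4.5.2, Part 2 reduction: "the dose of BMS-986158 should be reduced from 3.75 mg to 3 mg". For most entries, Table 4.5.2-1 asks only that a reduction be considered at the first event.
- 4.5.2, milder events: "Dose modifications, interruptions, or delays may occur in the setting of lower grade AEs", at the investigator's judgment and in consultation with the Sponsor/Medical Monitor.
- 4.5.3: interruption is recommended for diarrhea.

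**The concern.** The protocol otherwise treats CYP3A4 inhibition as a hazard. Section 1.4.3.5 attributes 66% of oxidative metabolism in vitro to CYP3A4 and 23% to CYP3A5, and acknowledges the potential for interactions. Exclusion 1(l) requires a washout before entry, and 3.4.2 bans grapefruit on study. Section 1.1.6 cites preclinical signs of a steep dose-toxicity relation or a narrow therapeutic margin.

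The waiver reopens that exposure for subjects who already have a drug-related AE. Two routes are open:
1. An AE below the mandatory hold triggers is treated with a strong inhibitor while dosing continues at 4.5 mg (loading) or 3.75 mg.
2. The AE resolves, and dosing restarts at 3.75 or 3 mg before the inhibitor course, or its effect, has ended.

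What is at stake is avoidable toxicity in individual subjects. No endpoint or decision rule depends on it.

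**Working it through.** **Does anything else close the gap?**
- Exclusion 1(l) is an entry washout: 1 week or 5 half-lives, whichever is longer. It sets no on-study rule.
- Section 3.4 limits CYP3A4-interacting androgen-deprivation agents in prostate cancer only.
- Section 3.4.2 covers grapefruit and Seville oranges, not medicines.
- Section 3.5 lists no inhibitor-specific reason to discontinue.
- Appendix 3 classifies inhibitors and gives no dosing instruction.
- The holds in 4.5.1 to 4.5.3 start with the AE and end when it recovers.

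None bars dosing or restart during inhibitor use.

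**When would exposure exceed that of 4.5 mg?** The plan states no figure to reproduce. Let f be the CYP3A share of clearance and I the fraction of CYP3A activity inhibited: 0.8 (Appendix 3's clearance threshold for a strong inhibitor) to 1.0. With linear PK, the steady-state AUC ratio is R = 1/(1 − f × I). Break-even is R = 4.5/dose, so f = (1 − dose/4.5)/I.

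| Dose | R needed | f at I = 0.8 | f at I = 1.0 |
|---|---|---|---|
| 3.75 mg | 1.20 | 0.208 | 0.167 |
| 3 mg | 1.50 | 0.417 | 0.333 |

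At 4.5 mg any sustained inhibition gives R above 1, but loading lasts only two weeks.

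**Illustrative size, by assumption.** The documents give no clinical value of f.
- In vitro share: 0.75 (main oxidative metabolite's share in human hepatocytes, 1.4.3.3) × 0.66 to 0.89 gives f = 0.495 to 0.6675. The lowest R is 1/(1 − 0.495 × 0.8) = 1.66 and the highest is 1/(1 − 0.6675) = 3.01. Relative to 4.5 mg, 3.75 mg gives 1.38 to 2.51 and 3 mg gives 1.10 to 2.01.
- A lower share, f = 0.25: R = 1.25 to 1.33. Then 3.75 mg gives 1.04 to 1.11 and 3 mg gives 0.83 to 0.89, with no overshoot at 3 mg.

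**Short courses.** A one-compartment model (half-life 39 h, 5 days on and 2 off, elimination rate divided by R) with the in vitro range gives weekly AUC relative to steady-state 4.5 mg:
- Continuing 3.75 mg: 1.14 to 1.48 in week 1 and 1.34 to 2.13 in week 2.
- Restarting at 3 mg after a two-week hold: 0.78 to 1.03 in week 1 and 1.05 to 1.64 in week 2.

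A brief overlap after restart at 3 mg therefore adds little or nothing.

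**The case against.** **No likely trigger.** The related AEs in 1.4.4 are mainly diarrhea, thrombocytopenia, nausea, anemia, vomiting, fatigue, raised bilirubin and neutropenia. The remedies the protocol names are antidiarrheals, anti-emetics, transfusions and growth factors, and none is on Appendix 3's strong list. That list is mostly azoles, macrolides and antivirals, and no drug-related infection is reported. For febrile neutropenia, where an anti-infective is most plausible, Table 4.5.2-1 already requires a hold at Grade 3 and discontinuation at Grade 4. This objection stands and makes the gap rare. It does not close the restart route.

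**Other safeguards.** Section 4.5.2 requires a documented causality assessment, which covers concomitant medicines, before any dose modification. Investigators may also hold more conservatively. Both help, but neither requires a hold or washout because an inhibitor is in use.

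**Intent.** The waiver suits corticosteroids and makes no sense for prior BET-inhibitor exposure, so it was probably not checked item by item. That explains the wording without changing what it permits.

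**Moderate inhibitors are unrestricted.** On the same in vitro shares, 50% to 80% inhibition gives R = 1.33 to 2.15, or 1.11 to 1.79 times 4.5 mg exposure at 3.75 mg. The protocol thus already tolerates modelled exposure in much of the same range. This is a fair limit on the urgency. The fix only restores the protocol's own line at strong inhibitors.

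**Conclusion.** The point holds as a small safety gap in the rule text: when a strong CYP3A4 inhibitor treats a drug-related AE, the protocol permits BMS-986158 dosing or restart during strong inhibition. That conclusion rests on the wording alone. Exposure above the 4.5 mg level is possible beyond the break-even shares shown, assuming linear PK and 80% to 100% inhibition. How far above is unknown, and the number of subjects cannot be estimated but is probably small.

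A reader might infer more, in three ways that the documents do not support:
- That 1.4 to 2.5 times the 4.5 mg exposure is to be expected at 3.75 mg. Those figures rest on in vitro shares, and in vitro work already mispredicted human PK: section 1.4.4.1 reports a free fraction of 0.1% to 0.2% against 3.9% determined preclinically, with lower clearance than anticipated.
- That subjects are over-exposed while the AE is active. Where dosing is held, no dose overlaps the inhibitor.
- That DLT or PK results are compromised, or that the SAP is in error. Nothing indicates enough cases to matter.

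Strong inducers fall under the same waiver, but they would lower exposure and are not part of this concern.

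**What to change.** In 3.4.1, state that the AE-treatment waiver does not cover strong CYP3A4 inhibitors unless BMS-986158 is held during their use and for the exclusion 1(l) washout. Add the same condition to the re-initiation sentence in 4.5.2. The inhibitor stays available to treat the AE; only BMS-986158 is withheld.

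The cost is two sentences in a protocol revision, with IRB/IEC approval under 9.1.1, and longer holds for a few subjects. With a 7-day washout, a 14-day course means 14 + 7 = 21 days off drug; the hold is longer if 5 half-lives of the inhibitor exceed a week. The 30-day rule needs no change: it concerns delayed AE recovery and already allows agreement to continue. No extra flagging of AEs or PK profiles is needed, and the SAP is unaffected.

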3.4.2 Other Restrictions and Precautions

Subjects may take the study drug with or without food, however it must be documented whether the drug was taken with or without (no food approximately1 hour prior and 2 hours after dose) food.

- Grapefruit and Seville oranges and their juices can inhibit CYP3A4 and should not be consumed while on study.
- Because of the potential for reproductive adverse effects, options for sperm and egg banking should be discussed with the subject, if appropriate.
- Subjects should be provided loperamide or lomotil at the first dosing visit, instructed on its use and counseled to contact their clinician at the first occurrence of diarrhea or loose stools.

Anti-Emetic and Anti-Diarrheal Medications

Supportive care may include premedication with anti-emetics to limit treatment-related nausea and vomiting. Subjects should receive medications for treatment-induced diarrhea, as outlined in Section 4.5.3.

Other Concomitant Medications

Anti-inflammatory or narcotic analgesics may be offered as needed. Packed RBC and platelet transfusions should be administered as clinically indicated.

3.5 Discontinuation of Subjects following any Treatment with Study Drug

Subjects MUST discontinue BMS-986158 if receiving monotherapy and both BMS-986158 and nivolumab if receiving combination therapy (and non-IP at the discretion of the investigator) for any of the following reasons:

- Subject's request to stop study treatment and/or participation in the study
- Any clinical AE, laboratory abnormality or intercurrent illness which, in the opinion of the investigator, indicates that continued participation in the study is not in the best interest of the subject
- Termination of the study by BMS
- Loss of ability to freely provide consent through imprisonment or involuntarily incarceration for treatment of either a psychiatric or physical (eg, infectious disease) illness
- Inability to comply with protocol

- Discretion of the investigator
- AEs requiring discontinuation as outlined in the Dose Modification section (See Section 4.5.2)
- Pregnancy
- Documented and confirmed PD as defined by RECIST v1.1 (for solid tumors, see Appendix 04), or Lugano 2014 (for hematoligic tumors see Appendix 09), or PCWG3 (for CRPC and NEPC see Appendix 12) unless participant meets criteria for treatment beyond progression (Section 3.6)

All subjects who discontinue investigational product (IP) should comply with protocol specified follow-up procedures as outlined in Section 5. The only exception to this requirement is when a subject withdraws consent for all study procedures including post-treatment study follow-up or loses the ability to consent freely (ie, is imprisoned or involuntarily incarcerated for the treatment of either a psychiatric or physical illness).

If study drug is discontinued prior to the subject's completion of the study, the reason for the discontinuation must be documented in the subject's medical records and entered on the appropriate CRF page.

3.6 Treatment Beyond Progression

Evidence supporting the continuation of BMS-986158 monotherapy in subjects with solid or hematologic malignancies beyond progression of their disease is lacking and therefore monotherapy treatment beyond progression will not be allowed. If combination therapy is pursued, subjects receiving BMS-986158 in combination with nivolumab will be permitted to continue on combination therapy beyond initial RECIST v1.1, Lugano 2014 (Appendix 9), or PCWG (Appendix 12) defined PD, as long as they meet the following criteria:

- Investigator-assessed clinical benefit and not having rapid disease progression
- Continue to meet all other study protocol eligibility criteria
- Tolerance of study drug
- Stable performance status
- Treatment beyond progression will not delay an imminent intervention to prevent serious complications of disease progression (eg, CNS metastases)
- Subject provides written informed consent prior to receiving any BMS-986158 plus nivolumab treatment using an ICF describing any reasonably foreseeable risks, discomforts, or other alternative treatment options

The assessment of clinical benefit should take into account whether the subject is clinically deteriorating and unlikely to receive further benefit from continued treatment. All decisions to continue treatment beyond initial progression must be discussed with the BMS Medical Monitor and an assessment of the benefit/risk of continuing with study drug must be documented in the study records. Subjects will be re-consented to explain the rationale for this ongoing treatment.

3.7 Post Study Drug Follow-up

In this study, safety is a key endpoint of the study. Post study follow-up is of critical importance and is essential to preserving subject safety and the integrity of the study. Subjects who discontinue study drug must continue to be followed for collection of outcome and/or survival follow-up data as required and in line with Section 5 until death or the conclusion of the study.

3.7.1 Withdrawal of Consent

Subjects who request to discontinue study drug will remain in the study and must continue to be followed for protocol specified follow-up procedures. The only exception to this is when a subject specifically withdraws consent for any further contact with him/her or persons previously authorized by subject to provide this information. Subjects should notify the investigator of the decision to withdraw consent from future follow-up **in writing**, whenever possible. The withdrawal of consent should be explained in detail in the medical records by the investigator, as to whether the withdrawal is from further treatment with study drug only or also from study procedures and/or post treatment study follow-up, and entered on the appropriate CRF page. In the event that vital status (whether the subject is alive or dead) is being measured, publicly available information should be used to determine vital status only as appropriately directed in accordance with local law.

3.7.2 Lost to Follow-Up

All reasonable efforts must be made to locate subjects to determine and report their ongoing status. This includes follow-up with persons authorized by the subject as noted above. Lost to follow-up is defined by the inability to reach the subject after a minimum of three documented phone calls, faxes, or emails as well as lack of response by subject to one registered mail letter. All attempts should be documented in the subject's medical records. If it is determined that the subject has died, the site will use permissible local methods to obtain the date and cause of death.

If investigator's use of third-party representative to assist in the follow-up portion of the study has been included in the subject's informed consent, then the investigator may use a Sponsor-retained third-party representative to assist site staff with obtaining subject's contact information or other public vital status data necessary to complete the follow-up portion of the study. The site staff and representative will consult publicly available sources, such as public health registries and databases, in order to obtain updated contact information. If after all attempts, the subject remains lost to follow-up, then the last known alive date as determined by the investigator should be reported and documented in the subject's medical records.

